RESPONSE: Aim 1: Determine the safety and feasibility of externally mounted magnetic devices for extended (> 1 week) home use for the management of early post-acute and chronic eyelid movement disorders. Aim 2: Collect preliminary data on the efficacy of external magnetic eye lid devices stemming from a variety of different pathologies.

OBJECTIVES

3) Your focused research question needs to be further refined into one or more study objectives. The study objective(s) should be single and quantifiable statement(s) that will allow you to answer your research question.

RESPONSE: Objective 1: Determine the safety and feasibility of externally mounted magnets for extended management of chronic eyelid movement disorders by measuring visual acuity and corneal and skin integrity and comfort over 8 weeks of wear.

HYPOTHESES

4a). Primary Hypothesis - Hypotheses are more specific than objectives and amenable to statistical evaluation. Your primary hypothesis is your statement of the hypothesized effect on the primary outcome measure. A hypothesis is worded very simply and written as 'testable' statements. Your experimental results will prove or disprove your hypothesis. Hypotheses are generally stated in the null form (H_0) as they have their basis in inferential statistics. Rejecting the null hypothesis increases our confidence, with a given level of probability, that there is a relationship between the variables being studied. However, a classic scientific hypothesis includes both a null and alternative (H_a) hypothesis.

**e.g. H_0 : Asthma prevalence rates are not different among children from low and high socioeconomic groups in Istanbul. H_a : Asthma prevalence rates are different among children from low and high socioeconomic groups in Istanbul.*

RESPONSE: Hypothesis: Externally mounted magnet systems will have a good safety profile defined as a mean decrease in visual acuity 1 line or less, high-mag photo documented skin-integrity rating better

than 2 (FDA industry scale), and no more than a two grade (NEI/Industry Workshop scale (Lemp, 1995)) worsening in superficial punctate keratitis on high mag photo-documented analysis.

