4b). Secondary Hypotheses - Although a study is usually based around a primary hypothesis, secondary hypotheses may also be pre-specified although based on outcomes of lesser importance or additional interest. As the primary hypothesis is usually the basis for statistical power calculations, secondary hypotheses with insufficient power will generally not lead to statistically robust conclusions.

RESPONSE: Externally mounted magnet systems will a) result in a significant improvement in the completeness of eye closure and opening as measured using image analysis of eye opening/closing with compared to without the device; b) will be comfortable to wear defined as a mean participant-reported comfort rating greater than or equal to 6/10 (or 60cm on a 100cm visual analog scale)

STUDY DESIGN

5) State the design of the research (e.g. randomized controlled study, cross-sectional survey, prospective or retrospective cohort/case-control).

**Whatever the study design, you need to ensure that you provide the reader with a clear statement and description of your proposed design. You may also explain why the particular study design has been chosen in preference to other possible designs (i.e. justification for choice of study design)*

RESPONSE: This is a prospective study. As the principal aim of this study is to determine safety and feasibility of extended home use, we will not attempt to randomize patients to a treatment and a placebo group nor will we have an age-matched control group. Participants will be made aware that a predicate device is commercially available and the magnet device is experimental.

ELIGIBILITY CRITERIA

6a). Inclusion Criteria - Inclusion criteria are the 'characteristics' that clearly describe the study population that are required for a subject to be included in the study. The criteria may be based on factors such as age, gender, the type and stage of a disease, previous treatment history, and co-morbid medical conditions. They may state appropriate criteria for admitting special 'at-risk' populations such as women of reproductive age, children or patients with disease states or organ impairment.

RESPONSE: Presence of an eyelid movement disorder for at least one eye, moderate cognitive function or better defined as greater than or equal to 18 out of 30 on a pre-screening of the Mini-Mental State Exam, age 5 or older

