RESPONSE: Skin integrity scales, change in ocular surface staining rating, participant comfort and satisfaction rating, and change in visual acuity. Skin integrity will be analyzed by applying a likert-type rating system to a high-mag/high-resolution photo documented image of the subject's lid skin. The number of adverse events will also be reported, defined as incidents which require temporary or permanent suspension of the participant's involvement. These include any broken skin, decrease in visual acuity more than 2 lines, worsening of corneal rating of more than 1.5 points or other ocular surface ratings more than 2 points, and comfort rating lower than 5/10 (or 50cm on the 100cm visual analog scale).

7b). Secondary Outcome(s) - Secondary outcome(s) are measures of additional or less important research interest. They may include additional clinical, psychological, economic, or safety outcomes (e.g. treatment related side effects/adverse events). However, as these endpoints are not used to calculate study power and sample size it is often not possible to draw robust conclusions from the results.

RESPONSE: Video analysis of eyelid biomechanics to measure the completeness of eye closure and opening compared to 1) no device, 2) relative to the contralateral side (if normal), 3) relative to the ptosis crutch or external lid weights. The same paired comparisons will be performed for the clinician and participant rating scale data. 3) Cognitive score on the MoCA will be analyzed for relationship to length of time in the study and satisfaction rating scores).

STUDY PROCEDURES

8) In this section you need to clearly and comprehensively describe exactly what will happen to participants once they are enrolled in your study. Depending on the study it might include how potential participants will be approached, when they will be randomized, the frequency and duration of visits or whether they are expected to self-complete a daily diary at home, the duration of the study or follow-up, and any measurements taken at each visit (e.g. questionnaires, physical measurements, biological samples).

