
week of the extended trial. If there are no complications after 1-week, a clinical decision may be made by the PI to decrease the visit frequency to the standard protocol.

9) Randomization (if applicable)

Include the method (including any software) used to generate the random allocation sequence. Describe type of randomization performed, ratio of assignment to groups, block size permutation and stratification if applicable. Explain the methods used to conceal group allocation until assignment. Also, include information on who will generate the allocation sequence and who will assign participants into their groups.

This section should also discuss if participants, the investigator, and those assessing/analyzing the outcome(s) will be blind (or masked) to group assignment or if the study will be an open-label study (investigators and subjects know their assigned group).

RESPONSE: There is no randomization counterbalancing will be used given the small sample size.

10) Study Specific Procedures: List all procedures (interventions, tests, surveys, etc.) to be performed ONLY for research purposes

RESPONSE: Specific to the study are the high magnification photo analyses of skin integrity, participant comfort and satisfaction ratings (visual analog scales), video analyses of the eyelid movements to measure the change in the amount of eye-opening and closing (volitional and reflexive opening and closing) with the magnetic devices compared to no device, comparisons of the amount of opening and closing with the magnetic devices compared to with the ptosis crutch or external lid weights, and efficacy ratings by both the clinician and participant.

11) Standard of Care Procedures: Clearly list all standard of care (standard therapy) procedures (interventions, tests, etc.) to be performed regardless of the subject's enrollment in the study, but that will be included in the research assessment.

RESPONSE: NA

MEASUREMENT TOOLS

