13) Sample size and statistical power - A sample size or power calculation should be performed. This calculation is used to estimate the number of subjects required to answer your primary study hypothesis with an accepted power. Conversely, it also allows you to estimate what power can be achieved with a limited number of participants. This number is calculated by specifying the magnitude of the effects that are expected (i.e. informed and clinically significant), variability of the measurements and the acceptable degree of type I and II errors. You need to specify the assumptions made for the calculation. It is recommended that you consult with a statistician for this section. Also keep in mind the estimated recruitment rate and whether you need to adjust for anticipated non-responders and losses to follow up.

RESPONSE: The primary hypothesis is that externally mounted magnet systems will have a good safety profile and will be feasible for home use therefore we will report the proportion of participants who have a safety issue and complete the trial. As this outcome is based on summary statistics and not comparisons between groups, a power calculation is not appropriate. Sample size was selected based on providing an as-broad-as-possible but feasible (within the time of the study) assessment of safety and feasibility. The sample size calculation for the secondary within subject comparison between devices is estimated at 10 for the ptosis group, using preliminary unpublished data for cranial nerve III palsy at Spaulding (n=7; efficacy for opening (mm) magnet vs. crutch was borderline with 7 participants p=0.08, and comfort had reached significance, p=0.05). A power calculation is not possible for the lagophthalmos group as preliminary data are only available for 3 participants. Power calculations for the secondary analysis will be re-evaluated during data collection.

14) Statistical methods - The statistical methods used for the study objectives/hypotheses (e.g. t-test, chi-squared, multivariate modeling) must be sufficiently detailed. If conducting a randomized controlled study, you should state whether methods will include an “intention to treat” (ITT) analysis, per protocol analysis, or both. An ITT analysis is preferred as it compares all subjects in the

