groups to which they were originally randomly assigned (despite withdrawal, treatment failure or cross-over). Consultation with a statistician is strongly recommended. [See Harvard Catalyst Statistical Consulting for more information.](#)

RESPONSE: Descriptive statistics will be calculated including a mean rating scale value for skin, corneal integrity, and visual acuity (logmar). A repeated-measures ANOVA will be used to determine if there is any change across visits/measurements. The completeness of opening and closing with and without the magnet and with the other devices will be compared using paired t-tests. As this is not a randomized design, ITT will not be used.

DATA SAFETY MONITORING PLAN (DSMP)

Complete question 15 **OR** 16 depending on the risk of the study. If your study is submitted as minimal risk and determined by the HSC to be more than minimal risk you will be asked to complete question 16 during the review process.

15) If the research is **no more than minimal risk**, please describe any provisions in place to ensure the safety of participants and the validity and integrity of data. If safety monitoring will occur a safety monitoring plan may include elements such as: parameters for safety review, the frequency in which safety review will occur, the person(s) responsible for safety review, and the plan (including the person(s) responsible) for reporting adverse events, protocol deviations, or noncompliance to the HSC and others (where applicable). Data monitoring may include the specific elements that will be reviewed (e.g., informed consent documentation, verification of the accuracy of data), the frequency of data monitoring, and the person(s) responsible.

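### Hypothesis 4b(a) claims a significant improvement in eye closure and opening, but no alpha, deciding contrast, recording or multiplicity rule says which paired t-test settles it

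*Combined protocol and SAP*

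**What the plan says.** Secondary hypothesis 4b(a) expects a "significant improvement in the completeness of eye closure and opening as measured using image analysis of eye opening/closing with compared to without the device". The analysis for it is one sentence in Section 14 (Statistical methods): "The completeness of opening and closing with and without the magnet and with the other devices will be compared using paired t-tests". The same section gives change across visits to a repeated-measures ANOVA.

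Other sections supply the dimensions of the comparison:

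- Section 7b lists three comparators without ranking them: no device, the other eye if normal, and the crutch or external lid weight. It adds that "The same paired comparisons will be performed for the clinician and participant rating scale data".
- Section 10 specifies "volitional and reflexive opening and closing" for the comparison with no device. It does not repeat that split for the comparison with the crutch or lid weight.
- Section 8 plans 25 participants with ptosis and 25 with lagophthalmos. Video is taken at baseline, at fitting, after the 20-minute trial and at follow-up.
- Section 13 sizes the magnet-versus-other-device comparison at 10 for ptosis, from pilot data on opening with magnet versus crutch.

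Aim 2 is to "Collect preliminary data on the efficacy of external magnetic eye lid devices". No section states an alpha, sidedness, a deciding contrast or a multiplicity rule.

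**The concern.** A claim of significance needs a rule, fixed beforehand, for which result establishes it. Hypothesis 4b(a) fixes the comparator (no device) and nothing else. It does not say whether closure and opening must both improve or whether one is enough. It also leaves open which lid action counts, whether each disorder group makes its own claim, and which recording is the with-magnet value.

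The last choice is wide for ptosis. Section 8 has the fitting try 10 coating thicknesses, two lid-magnet polarities and four spectacle-magnet orientations.

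The study is open and uncontrolled, so the team that makes these choices could do so after seeing the videos. A published statement that the device significantly improved lid function would then carry more than the usual risk of being false, and readers could not tell how much more.

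**Working it through.** **The plan's own figure.** Section 13 gives n = 10 for magnet versus crutch, without alpha, power or sidedness. The pilot (n = 7, p = 0.08, taken as two-sided) gives t = 2.104 on 6 df, so the standardised paired difference is 2.104/√7 = 0.795.

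- Two-sided 5%, 80% power: 15 by the t distribution, 13 by the normal approximation.
- One-sided 5%, 80% power: 12 by the t distribution, 10 by the normal approximation.

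The figure of 10 can be reached under some assumptions and is not disputed. What matters here is that it belongs to magnet versus crutch, whereas 4b(a) concerns magnet versus no device.

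**Inputs for the error rate.**

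- Alpha: not stated. I assume 5%, in line with the pilot remark "comfort had reached significance, p=0.05".
- Sidedness: not stated; two-sided assumed.
- Groups: two of 25, independent of each other (Section 8).
- Correlation between tests within a group: unknown; 0 to 0.8 shown.
- All null hypotheses true.

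**Formula.** A two-sided 5% test favours the magnet falsely with probability 0.025. For k independent tests, the chance of at least one false favourable result is 1 − 0.975^k, and of at least one significant result in either direction 1 − 0.95^k. For correlated tests I simulated paired t-tests on normal differences (n = 25, equal correlation within a group, 200,000 replicates).

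| Tests that may support the statement | k | Correlation 0 | 0.5 | 0.8 |
|---|---|---|---|---|
| *False favourable result, versus no device* | | | | |
| One test in one group | 1 | 2.5% | – | – |
| One test in each group | 2 | 1 − 0.975² = 4.9% | – | – |
| Opening and closing, two groups | 4 | 1 − 0.975⁴ = 9.6% | 8.8% | 7.7% |
| The same, volitional and reflexive separately | 8 | 1 − 0.975⁸ = 18.3% | 15% | 11% |
| *Any significant result, either direction* | | | | |
| Opening and closing, versus no device and versus other device, two groups | 8 | 1 − 0.95⁸ = 33.7% | 29% | 22% |

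The first four rows bear on 4b(a). The last row describes Section 14 as a whole: how often some significant efficacy result would appear if the device did nothing.

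**If both movements must improve.** The false favourable rate within a group cannot exceed that of one test, 2.5%. Over two groups it is at most 4.9%, so there is no inflation within a group. This reading fits the devices poorly, however. It would require closing to improve in ptosis, where Section 8 warns that a magnet with too thin a coating prevents proper blinking.

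**The case against.** The strongest reply is that efficacy is secondary, Aim 2 calls it preliminary, and the primary outcome is descriptive, so formal error control is not expected. That limits the severity, and it stands. It does not settle the point, because 4b(a) is still worded as a significance claim, and neither 4b nor Section 14 calls the tests exploratory.

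A second reply is that 4b(a) already names its comparator. That is right, and it narrows the problem. A reader might infer that any p < 0.05 in the whole set would meet 4b(a). The text does not support this: a result against the crutch, lid weight or other eye, a result on a rating scale, or a significant worsening cannot satisfy a claim of improvement over no device.

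Three further inferences are tempting and should not be drawn.

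- The tests are not shown to be multiplied over visits. Section 14 assigns change across visits to the ANOVA. The gap is that no recording is named for the t-tests.
- The volitional and reflexive split cannot be applied to every comparator, since Section 10 attaches it only to the no-device comparison.
- A chance significant improvement is not shown to be likely. For the 4b(a) tests the favourable rate is at most about 18%.

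**Conclusion.** The concern holds in this limited form. Hypothesis 4b(a) makes a significance claim with no defined error rate, and the one contrast that was sized is not the one claimed. If either movement in either group counts, the false favourable rate is about 8 to 10%. With the lid actions tested separately it is about 11 to 18%. One test per group gives about 5%, and a single test 2.5%. With the other-device comparisons of Section 14 included, some significant result in either direction is expected in about 22 to 34% of such studies.

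These figures assume two-sided 5%, 25 per group, equal correlations of 0 to 0.8, no true effect, and that one favourable movement is enough. The documents confirm none of these except the group size. Freedom to pick the with-magnet recording is not in the figures and could only add to them. The effect is on the wording of a secondary result; the safety and feasibility conclusions are untouched.

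**What to change.** In Sections 4b, 7b and 14:

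1. Name one key contrast per disorder group: completeness of the movement that the disorder impairs (opening for ptosis, closing for lagophthalmos), magnet versus no device, for one stated lid action.
2. Take it from one pre-stated recording at the fitting visit, in all fitted participants. State which magnet configuration that recording shows, so that it is not picked from several by result. The 1-week visit is unsuitable. Section 8 lets participants reach it only after examiner scores of at least 6 on blink mechanics and efficacy at both the immediate and the 20-minute trial, so they are selected for apparent efficacy.
3. State the alpha: two-sided 5% in each group if each makes its own claim, or 2.5% in each if one claim is made across both. The latter holds the overall two-sided rate at 1 − 0.975² = 4.9%.
4. Label every other movement, lid action, comparator, visit and rating comparison exploratory, in line with Aim 2. Report mean paired differences with 95% confidence intervals and no significance claims. This includes the other-device comparison: Section 8 describes the lid weight only at fitting and describes no crutch fitting.

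The cost is a few sentences and no extra participants. Fitting-visit video is already planned; at most, one further recording of about a minute is needed if the chosen configuration is not otherwise filmed. Fewer comparisons can be called significant, and the key contrast speaks to the immediate effect, leaving durability to the descriptive results. Power is unlikely to suffer: at the pilot effect of 0.795, 25 per group gives about 97% at two-sided 5%. That effect is for magnet versus crutch in ptosis, so the figure is only illustrative here.
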